A secondary measure will be the change in DVA with x1.5 viewing, with the prediction that DVA with the moving scene will improve after the VOR has adapted to that visual-vestibular condition and that the improvement in DVA will correlate with that of the VOR. Pre- and post-adaptation VOR gains will be compared using a paired t-test, employing a power transformation if the assumption of normality is not satisfied. Most of the software that will be required for data analysis has already been written by the PI or other members of the laboratory.

Vestibular patients will complete questionnaires (Dizziness Handicap Inventory, Activity-based Balance Confidence) to assess the extent and functional impact of their symptoms, but these will not be outcome measures for the study.

Subjects will rate their feelings of motion sickness on a 0-10 scale following each playing session.

11. Provide a BRIEF DESCRIPTION of how the estimated number of study subjects needed for this research was determined

- *If this is a quantitative study provide the method of determining sample size estimates.*
- *If multiple studies are planned provide a power analysis or justification for each one.*

This is an unpowered pilot study that is funded under the SPiRE mechanism. The number of subjects was chosen to provide adequate preliminary data to support a funding application for a larger clinical trial.

12. The research involves the following procedures conducted by and for what purpose:

PROCEDURE	PERFORMED BY:		PROCEDURE IS:	
	Research Staff	LSCDVAMC Clinical or Support Staff	Standard of Care*	For Research Purposes Only**
Audiotaping / Videotaping Attach VA Form 10-3203 REQUIRED ONLY FOR IN-PATIENT AND OUT-PATIENT SUBJECTS				
Biopsy				
Blood collection				
Chart review – prospective				
Chart review – retrospective				

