13. Please describe the research design and all study related procedures.

- Describe **ALL PROCEDURES ASSOCIATED WITH THIS RESEARCH**. This includes standard of care and research procedures.
- For complex studies please include diagrams and tables. Be sure to describe when each procedure will be performed. Be sure to provide information for **each cohort, including normal controls**.

The hypothesis of the study is that computer-game-based incremental adaptation will induce robust VOR motor learning and will provide an engaging platform for vestibular rehabilitation. The hypothesis will be tested with two specific aims:

Aim 1 (Healthy volunteers) will test the efficacy of our game to elicit VOR motor learning in 18 healthy volunteers with no history of vestibular disease. Each subject will play the game

twice for sessions of 300 trials each (about 30 minutes of game playing). In one of these sessions, the game will be structured to increase VOR gain in a single step and in the other session, the gain increase will be advanced incrementally to the same final target. The hypothesis predicts that the latter paradigm will lead to more efficient learning. The specific procedures for Aim 1 will be as follows:

Each subject will participate in two separate sessions on different days. In one session, the full visual-vestibular mismatch ($\times 1.5$) will be introduced at the start of the game (paradigm A) and in the other session scene motion will be gradually adjusted to adapt the VOR incrementally (paradigm B). Each session will consist of 300 trials. To eliminate an order effect, the paradigm order will be randomized across the group of subjects: half will do paradigm A first, and the other half will begin with paradigm B.

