Aim 2 (Vestibular Patients) will test the playing experience of 12 subjects with peripheral vestibular disorders and will obtain preliminary data regarding efficacy and feasibility of the game for clinical vestibular therapy. The experimental protocol will be similar to that of Aim 1 (see above), with recording of both eye and head positions during VOR testing and game playing. The active and passive VOR, as well as DVA, will be recorded before and after the game. For each subject, we will begin by determining the baseline VOR gain. The game will then be played with a scene motion that corresponds to a VOR gain that is 20% higher than the baseline value for active rotation, separately set for each direction of head rotation. For example, if a patient with left vestibular hypofunction has a baseline VOR gain of 0.5 for active turns to the left, then scene motion will be set to $\times 0.6$ viewing (20% higher than 0.5). The subject will play the entire game with this condition, rather than advancing the difficulty as in Aim 1, because in clinical rehabilitation the difficulty is advanced more slowly, in a series of sessions over weeks of therapy.

Data Acquisition: We will record head position using our 3-D magnetic-field coil system, long considered the gold standard for measuring eye and head rotations, due to its accuracy and high signal-to-noise ratio. Our system has large field coils (6 ft cube), which provides an adequate area of homogeneity at the center of the field for head-free recordings. Eye movements will be recorded simultaneously using a lightweight head-mounted video-oculography (VOG) system (IScan) that records 2-D eye position at 240 Hz. Analog VOG pupil-tracking data are saved together with the head coil signals in the same file for reliable synchronization of eye and head. Finally, calibrated head positions will be calculated in real time (via Simulink Real Time) and sent over UDP to the gaming computer to drive scene motion at the specified visual-vestibular mismatch. A computer-generated log file will record data from each trial: instructed direction of head movement; optotype size, orientation, and on-time; the subject's key-press response; and a time-stamp for synchronization with the recorded head and eye position data.

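### Does it matter that the only stated viewing condition for dynamic visual acuity, x1.5, fits the healthy volunteers of Aim 1 but not the patients of Aim 2?

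*Combined protocol and SAP*

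**What the plan says.** Section 3, item 10 makes passive and active VOR gain the primary outcomes. On DVA it says "A secondary measure will be the change in DVA with x1.5 viewing". The expectation attached to this measure is "DVA with the moving scene will improve after the VOR has adapted to that visual-vestibular condition". Item 10 also expects the change in acuity to track the change in the reflex. The only named test concerns gain: "Pre- and post-adaptation VOR gains will be compared using a paired t-test".

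Item 13 sets the training conditions. In Aim 1 one session applies x1.5 from the start, and in the other "the gain increase will be advanced incrementally to the same final target". For Aim 2 it says "The experimental protocol will be similar to that of Aim 1" and, later, "The active and passive VOR, as well as DVA, will be recorded before and after the game". The Aim 2 setting is individual: "The game will then be played with a scene motion that corresponds to a VOR gain that is 20% higher than the baseline value". The baseline meant here is the gain during active turns, and a patient can have a different setting to each side, since it is "separately set for each direction of head rotation". The worked example takes a baseline gain of 0.5 to x0.6 viewing, and the setting is held for the whole game.

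Item 9 has each patient play weekly for four weeks. Item 11 describes the study as an unpowered pilot. Item 20 stops Aim 2 enrolment at 6 unilateral and 6 bilateral patients with complete data.

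**The concern.** Item 10 justifies DVA by a match between test and training: acuity should improve in the condition to which the reflex has adapted. The match holds in Aim 1, where both sessions end at x1.5. It does not hold in Aim 2, where a patient would train at x1.5 only with a baseline gain of 1.25.

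Two readings are possible, and each seems to leave a defect. If item 10 covers both aims, patients are tested in a condition on which they never train. If it covers Aim 1 only, DVA in patients has no stated condition and no stated summary. The separate Data Analysis paragraph in item 13 does not help, because it does not mention DVA.

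Aim 2 is meant to supply preliminary efficacy data for a larger trial. If the condition were chosen late, or varied between patients or sessions, the DVA changes would be hard to interpret or pool, and no later analysis could repair that.

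**Working it through.** **Inputs.** From item 13: training setting = 1.2g, where g is baseline active gain, and the example g = 0.5. From item 10: DVA condition x1.5. From items 9 and 20: 12 patients and 4 weekly sessions. Every other value of g below is an assumption.

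**The plan's own figure.** 1.2 × 0.5 = 0.6, as stated.

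**Where the conditions coincide.** 1.2g = 1.5 gives g = 1.5/1.2 = 1.25. For assumed gains of 0.1 to 1.0 the trained settings run from x0.12 to x1.20, so x1.5 is not the trained condition for any of them.

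**How much is affected.** One pre-post pair per patient gives 12 × 2 = 24 DVA measurements. A pair at every weekly session gives 12 × 4 × 2 = 96. Both counts assume one score per test. The plan does not say which applies.

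**Is one condition clearly better?** Take signed slip as viewing factor minus gain. Full adaptation from g to 1.2g changes it by 0.2g whatever the viewing factor. At g = 0.5 the change is 0.10:

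| Viewing condition | Slip before | Slip after | Change | Share removed |
|---|---|---|---|---|
| x0.6 (trained) | 0.10 | 0.00 | 0.10 | 0.10/0.10 = 100% |
| x1 (natural) | 0.50 | 0.40 | 0.10 | 0.10/0.50 = 20% |
| x1.5 | 1.00 | 0.90 | 0.10 | 0.10/1.00 = 10% |

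The absolute change is equal and the share removed differs. The documents give nothing to convert either into acuity, so no loss of acuity can be shown for any condition.

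Each candidate has a drawback:

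- **Trained setting.** This follows item 10's reasoning most closely, but the condition differs between patients and between directions of rotation.
- **x1.** This reflects everyday viewing and lies nearer the trained target than x1.5 when |1 − 1.2g| < 1.5 − 1.2g, that is g < 1.25/1.2 = 1.04. It is also untrained. The size of slip at x1 grows after full adaptation once 1.2g − 1 > 1 − g, that is g > 2/2.2 = 0.909. At g = 1.0 it goes from 0 to 0.20; at g = 0.9 it falls slightly, from 0.10 to |1 − 1.08| = 0.08.
- **x1.5.** This is far from the trained target for a low gain (1.5 − 0.6 = 0.90 in the example). It does allow comparison with Aim 1, and slip there falls with full adaptation for every g below 1.25 (at g = 1.0, from 0.50 to 0.30).

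**Does the plan put patients at x1.5?** Item 10 refers to a single experiment and names the Aim 1 mismatch. Where it turns to patients, for the questionnaires, it says so. The comparison of Aim 2 with Aim 1 in item 13 cannot carry over a DVA condition, because the Aim 1 procedures there do not mention DVA. Item 14 adds that the aims have different objectives. The mismatch is therefore not written into the plan; what is left is an omission.

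**The case for a change.** The best case for a change is this. The questionnaires are expressly not outcomes, so DVA is the only named measure of functional vision in patients. A test condition, unlike an analysis method, cannot be mended afterwards. The form asks for procedures for each cohort and for methods suited to the data. Item 10 also mentions vestibular patients, so reading it as Aim 1 only is not beyond argument. Two or three sentences would settle the matter without an added visit.

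Much of this stands as description. The Aim 2 condition and summary are not written down, and writing them down would do no harm. It does not show that the plan goes wrong. DVA is measured before the game as well as after, so a condition has to be chosen before a patient's first post-game value exists, and a pre-post change makes sense only if it is held. Aim 2 attaches no prediction of its own to DVA, and a descriptive summary in 12 patients is ordinary in a pilot. The missing test is not peculiar to Aim 2 either: item 10 names no DVA test for Aim 1. Requiring x1, or ruling out x1.5, would exchange one untrained condition for another.

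**Conclusion.** No change is called for. Item 10's DVA condition and prediction belong to Aim 1, and the plan leaves unstated how DVA is viewed and summarised in Aim 2. That is missing detail in a secondary measure, which the investigator can fill sensibly, and none of the three obvious conditions is clearly superior.

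The reach is 24 to 96 DVA measurements in 12 patients. The effect in acuity units cannot be computed from the documents. The primary gain outcomes, and the Aim 1 comparison of incremental with single-step adaptation, do not depend on it.

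This rests on three assumptions: that item 10's DVA sentence is read as Aim 1, that slip is modelled as viewing factor minus gain with full adaptation to the trained target, and that the investigator keeps one approach to the Aim 2 DVA test throughout. Only the baseline gain of 0.5 comes from the plan. If a later trial made DVA in patients an outcome in its own right, its protocol would have to state the viewing condition.

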In the first aim, we will test the ability of the game to induce VOR plasticity (to modify the gain of the VOR) in subjects with intact vestibular function. To do this, we will have subjects play the game with a visual condition (background movement that is tied to head velocity) that requires them to make a larger than normal eye movement when the head rotates. Such visual-vestibular mismatch has been shown in the past to lead to an increase in the gain of the VOR, even when tested in the dark. Our hypothesis is that incremental adaptation (increasing the amount of visual-vestibular mismatch gradually in a series of steps) will be more effective in inducing this plasticity, so we will compare the change in gain with this paradigm to that induced by imposing the full amount of visual-vestibular mismatch all at once.

In the second aim, we will obtain preliminary data regarding the efficacy and feasibility of the game for clinical vestibular rehabilitation. Patients with peripheral vestibular hypofunction will play the game with the degree of visual-vestibular mismatch customized for their individual level of impairment. They will provide feedback regarding the game and their tolerance of the playing experience. Each subject will play once a week for four weeks. This will give us preliminary data regarding short-term VOR learning in these patients.

10. Describe the means of analyzing the data and evaluating the results.

- *State the anticipated methods to be used for analysis and interpretation of the data.*
- *The methods must compliment the design of the study and the nature of the data which is being collected.*

Data Analysis: The primary outcome measures for this experiment are the passive and active VOR gains. The VOR gain will be calculated for each subject and condition using an

optimization procedure in MATLAB that fits eye velocity to delayed head velocity. In addition to assessing the slow-phase gain change, we will examine “non-vestibular” components of the post-adaptation eye movements; for example, an increase in saccades during the head rotation (covert saccades) may also contribute to gaze stability.

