19. Anticipated duration of entire study reported in years: The study as proposed is expected to last for 6 years (a one-year extension was approved by VA RRD, an additional no-cost extension will be requested to complete enrollment and study procedures, follow-on years for additional data analysis, including preparation of the next funding proposal).

20. Estimated number of subjects to be studied at the LSCDVAMC or charts/records to be reviewed.

- *Provide answers for each cohort including normal controls; (patients, family members, treating physicians,):*

AIM 1: Healthy volunteers: 30 (per the funded protocol, enrollment will be stopped when completed data are obtained for 18 subjects)

AIM 2: Vestibular Patients: 20: (per the funded protocol, enrollment will be stopped when completed data are obtained for 6 subjects with unilateral hypofunction and 6 subjects with bilateral hypofunction)

Note that it may be necessary to enroll more than the targeted number of subjects in order to reach the goals, if some subjects drop out before completing the full study.

21. Estimated number of subjects to be studied or charts/records to be reviewed at all sites

- *Provide answers for each cohort including normal controls; (patients, family members, treating physicians,)*

N/A SINGLE SITE

22. Duration of individual subject participation

Provide answers for each cohort including normal controls; (patients, family members, treating physicians,). Each experimental session is expected to last approximately one hour. Healthy volunteers who are the subjects of Aim 1 will each participate for two recording sessions. Vestibular patients who are the subjects of Aim 2 will each participate for four sessions. Analysis of subjects' data will continue for the duration of the study.

Chart/record review N/A

23. Age range of subjects

- *provide answers for each cohort, including normal controls:*

Adults 18 years or greater

Specific age range (list age range): 18-75

Children –waiver from VACO: **attached** **pending- provide submission date:**

***Contact AO/Research [contact] for guidance..*

24. Which of the following will be recruited or reviewed for this study (check all that apply)?

Veteran Inpatients

Men

Veteran Outpatients

Women

Veteran Families

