No Yes- explicitly describe your process for identifying and/or recruiting these patients: (address all cohorts): Patients will be recruited by [name] from the VANEOHS neurology clinic or will be referred by other providers. As above, patients will also be identified by review of CPRS records of patients seen in those clinics.

29. In addition to the consent form will any other materials be given to the subject?

- N/A Chart/data review
- No Yes- check all that apply and submit for IRB review:
 - Letter
 - Information Sheets
 - Questionnaire, Survey, Diary
 - Other (flyer, brochure, describe): The recruitment flyer and recruitment letter with study information will be used to advertise the study to potential subjects.

30. Please list by bullet point inclusion/exclusion criteria for the study.

- *Entry criteria should be as detailed as necessary to define the subject population(s) under study and reduce confounding design. Include precise criteria for age, gender, and other relevant factors.*
- *List specific exclusion criteria which could interfere with the study design or place a subject at risk during the study.*
- *Provide answers for each cohort, including normal controls.*

AIM 1: Healthy Volunteers

- Adults age 18-75
- No history of vestibular disease
- Equivalent visual acuity at testing distance of 20/30 or better without or with spectacles

AIM 2: Vestibular Patients

- Adults age 18-75
- Peripheral vestibular hypofunction (unilateral n=6, bilateral n=6)
- No central vestibular disorder
- Equivalent visual acuity at testing distance of 20/30 or better without or with spectacles

N/A Chart/data review

31. By role, (PI, Coordinator, etc.) who will assess for eligibility and how will this be accomplished?

The PI will assess all potential subjects for eligibility by personal interview and a brief clinical examination. Veterans who are potential subjects for Aim 2 will be further assessed for eligibility by a review of their medical record pertaining to the diagnosis of peripheral vestibular disease.

32. Are any subjects excluded on the basis of race, ethnic group, understanding of English, socioeconomic status, education, gender, or pregnancy?

- *Note: It is appropriate to indicate that you do not anticipate encountering potential subjects who do not speak English based on the population to be studied*

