- By protecting researchers and institutions from being compelled to disclose information that would identify research subjects, Certificates of Confidentiality help achieve the research objectives and promote participation in studies by assuring confidentiality and privacy to subjects.
- For more information, see <http://grants1.nih.gov/grants/policy/coc/index.htm>.

39. Is this project principally concerned with the collection of sensitive information such as sexual attitudes, use of drugs or addictive products, and illegal conduct that would need to be protected against subpoena or forced disclosure in order to protect subjects?

No

Yes- will an application for a *Certificate of Confidentiality be submitted to the National Institute of Health upon IRB approval (or approval contingent on the issuance of such a certificate)?

Yes No provide a justification as to why a Certificate of Confidentiality will not be obtained:

40. Describe all procedures that minimize risks, please include study and standard of care procedures:

- If the subject becomes too motion sick, he/she may stop the experiment at any time. Both the head movements and the visual stimulation that are a part of this study are comparable to what is experienced in everyday life and in routine clinical examinations.
- Research data will be secured in several ways. First, all paper forms, including consent forms, will be kept in a locked cabinet in the PI's locked office, within the Daroff-Dell'Osso Ocular Motility Laboratory. Second, electronic data will be stored on encrypted drives (non-networked encrypted drive in the Daroff-Dell'Osso Ocular Motility Laboratory and encrypted VA networked drive [Ocular Motility Research Drive]). Moreover, the only identifiers associated with these binary data files are the subject code and the timestamp indicating when the files were created and the data was collected. No more explicit subject identifiers, such as name, birthdate, SSN, or any clinical diagnosis information, are contained in these coded files.

41. Describe alternative procedures or course of treatment, if any, which might be advantageous to the subject. State if no alternatives exist or if this is not a treatment study.

This is not a treatment study.

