***CHECK BOX IF THIS IS A MINIMAL RISK STUDY SKIP TO #65**

63. Safety monitoring for this greater than minimal risk project will include:

- Data Safety Monitoring Board:**
- Data Monitoring Committee**
- Other**

- *Attach the plan or provide details including whether committee is independent from the study sponsor, how often it meets, whether written reports are available, etc*

64. Describe the plan for on-site data monitoring by the sponsor, contract research organization (CRO), or other independent body:

- **Research Office must be notified of all on-site monitoring visits.*

65. Conditions that may result in removal of subjects from the research (check all that apply):

 Medical condition unchanged	 Medical condition worsened
 Serious adverse event	 Intolerable complications
 Pregnancy	 Investigator's clinical judgment
 Subject withdrawal	 Subject uncooperative or noncompliant
 Study closure by sponsor or FDA	 Refusal to suspend breast-feeding
 Other-describe:	 Not Applicable

66. If a subject withdraws or is removed from the study, describe the potential risks of early withdrawal and the procedures in place to minimize these risks:

Section 9 – FDA-Regulated Drugs/Biologics

NOTE: If this research involves the use of any drugs or biologics, the study is subject to the Food and Drug Administration (FDA) regulations.

- Documentation of FDA approval for the experimental use of these agents must be provided for review (industry sponsored protocol listing the IND number, letter from the FDA, letter from industry sponsor, or other document and/or communication verifying the IND for this study).
- All drug/biologic products must be dispensed and tracked through the LSCDVAMC Research Pharmacy.
- An M.D. must be part of the Research Team for all studies that involve the use of a device or drugs.
- The LSCDVAMC Pharmacy and Therapeutics (P&T) Committee must approve: (1) Studies of investigational drugs (2) research involving an FDA-approved drug used in a non-approved manner, and (3) an FDA-approved drug, used as approved, when its use is part of a research protocol.

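### Does counting Aim 2 by completers, with drop-outs replaced, bias the tolerance and feasibility results?

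*Combined protocol and SAP*

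**What the plan says.** Item 20 (Section 4) estimates 20 vestibular patients and sets the recruitment end point: "enrollment will be stopped when completed data are obtained for 6 subjects with unilateral hypofunction and 6 subjects with bilateral hypofunction". A note adds that enrolment may exceed the target "if some subjects drop out before completing the full study". Item 13 (Section 3) says Aim 2 "will test the playing experience of 12 subjects with peripheral vestibular disorders", and the Aim 2 entry criteria in item 30 repeat six unilateral and six bilateral.

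On tolerance, item 9 says of the patients: "They will provide feedback regarding the game and their tolerance of the playing experience". They play once a week for four weeks. Item 10 adds: "Subjects will rate their feelings of motion sickness on a 0-10 scale following each playing session". Item 40 says: "If the subject becomes too motion sick, he/she may stop the experiment at any time". Item 65 ticks serious adverse event, investigator's clinical judgment, subject withdrawal and "Subject uncooperative or noncompliant" as possible grounds for removal.

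Item 10 names passive and active VOR gain as primary outcomes and the change in DVA as secondary. Its one stated test is a paired comparison of VOR gain before and after adaptation. Item 11 describes an unpowered pilot meant to support a funding application for a larger trial.

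**The concern.** The number whose playing experience is to be tested (12) equals the number of completers required (6 + 6). Read together, items 13 and 20 suggest that the group described for tolerance is the group that lasted all four sessions. Motion sickness is both a reason to stop and the thing being rated, so dropping those who stopped would remove the least favourable evidence. Completion among completers is 100% whatever happened to the others.

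The plan does not state a denominator for tolerance or feasibility. It does not commit to reporting how many stopped, when and why, and it does not say whether a session cut short receives the 0-10 rating. If only the 12 were reported, tolerability could look too good and the larger trial would have no completion rate to plan on.

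**Working it through.** **Consistency of the plan's figures.** 6 + 6 = 12 agrees across items 13, 20 and 30. There is no power calculation to reproduce. The enrolment estimate leaves 20 − 12 = 8 places beyond the target, or 8/20 = 40%. The plan states no drop-out rate.

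**How large the gap could be.** Let m be the number of non-completers alongside 12 completers. Non-completion among starters is m/(12 + m), with an exact (Clopper-Pearson) 95% interval:

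| m | Starters | Non-completion | 95% interval |
|---|---|---|---|
| 0 | 12 | 0/12 = 0% | 0 to 26.5% |
| 4 | 16 | 4/16 = 25% | 7.3 to 52.4% |
| 8 | 20 | 8/20 = 40% | 19.1 to 63.9% |

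Sampling until 12 have completed is strictly inverse sampling. The lower limit is then the 2.5% quantile of a Beta(m, 12) distribution instead of Beta(m, 13). It moves from 7.3% to 7.8% for m = 4 and from 19.1% to 20.3% for m = 8; the upper limits do not change. The difference is immaterial.

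The range shows what is possible and is not a forecast. The 20 is an estimate, not a cap. Enrolment stops only when both groups reach six, so one group may exceed six. Some of the surplus may be unusable recordings, not patients who stopped. With m = 0 there is nothing to correct.

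**Whether the plan's rules produce the biased summary.** Three questions decide this.

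1. *Does any section limit the tolerance results to completers?* No. Item 20 answers a question about how many subjects will be studied and says when enrolment ends. The 12 in item 13 and the six per group in item 30 are targets of the same kind. Item 22 says analysis of subjects' data continues for the duration of the study, without restricting it to those who finish.
2. *Do data exist for patients who leave early?* Mostly. The rating in item 10 applies to subjects, after each session. A patient who leaves after session 1, 2 or 3 has already contributed one, two or three ratings. What is unclear is the rating for a session broken off midway.
3. *Does stopping for motion sickness necessarily mean leaving the study?* Not on the wording. Item 40 lets a subject stop the experiment, and item 48 uses the same word for a visit to the laboratory. A patient could end one session and return for the next.

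Following the written rules therefore does not by itself yield a completers-only tolerance result. That would need a further step, discarding ratings already collected, which the plan nowhere takes.

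**The case for a change.** The strongest case for a change is that silence leaves the choice of denominator open until the results are known. The stakes are also not trivial for this study: tolerance and feasibility are Aim 2 objectives, the study hypothesis includes the game being an engaging platform, and the data are to support a larger trial for which a completion rate is a basic input. Unpowered status does not answer this, since nothing here depends on power. The remedy would be a few sentences, with no added patients or visits.

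Much of that stands. The denominator, the reporting of stops and the handling of an interrupted session are all unwritten, and a completers-only report would mislead if patients had stopped because of intolerance. But the harm is conditional on a reporting choice that the plan does not make. Writing the denominator down would leave the recruitment rule, the data from completed sessions and the VOR analysis as they are. No tolerance test or go/no-go threshold depends on it, and the motion-sickness rating is named as neither a primary nor a secondary outcome.

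**Conclusion.** This is a gap in reporting detail that analysts can be expected to fill sensibly; it is not an error in the plan. Recruiting to a fixed number of completers is a reasonable way to secure 6 + 6 usable data sets in a small pilot. It does not prevent an account of everyone who started, with the number completing each session and the reasons for stopping.

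The most that could be hidden, taking the estimate of 20 at face value and every surplus patient as a non-completer, is 8/20 = 40% non-completion (19.1 to 63.9%). With no drop-outs it is zero. The conclusion assumes that completed data for Aim 2 means all four sessions, which the plan does not define, and that ratings already taken from early leavers are kept, which nothing in the plan contradicts. If a report of this study gave tolerance for the 12 completers only, the criticism would apply to that report.
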